4. STUDY DESIGN

This is a single-center, randomized, sham-controlled, double-blind clinical study to investigate the feasibility of delivering RS-tDCS sessions for high-risk patients for suicide in the days following discharge from the CPEP or inpatient unit which they were admitted with SI or attempt. We plan to assess up to 80 adult patients for eligibility over 12 months of which 20 will be enrolled and randomized. Clinical assessments will be performed at baseline, post-treatment day 14 (14 days after the first RS-tDCS session), and follow-up day 30 and 60 (30 and 60 days after the first RS-tDCS session, respectively).

All study outcome measures are described in Table 1.

Time points		in-person	remote	
	Measures		S1 to S10	C14, C30, and C60
Eligibility screening		Х		
Informed consent		Х		
Enrollment		Х		
		Baseline		
Demographic data		Х		
General medical history		X		
Orientation tDCS session		X		
Loan agreement		Х		
	Feasibility		X*	
	C-SSRS	X		Х
	RRS	X		Х
	CAST	Х		Х
	MADRS	Х		Х
	C-SSRS SV		X	
	Side effects questionnaire		X	
	Treatment emergent event review		Х	Х
	Acceptability questionnaire		X**	
	Blinding assessment		X**	

Table 1. Study's time points and measures.

C14, C30, and C60: clinical assessments at post-treatment day 14, follow-up day 30 and follow-up day 60; CAST: The Concise Associated Symptoms Tracking; C-SSRS: The Columbia-Suicide Severity Rating Scale; C-SSRS SV: The Columbia-Suicide Severity Rating Scale – screening version; MADRS: Montgomery-Asberg Depression Rating Scale; RRS: Ruminative Responses Scale; S1 to S10: remotely supervised transcranial direct current stimulation (RS-tDCS) sessions one to ten.

*Number of completed RS-tDCS sessions per participant within three weeks of the study.

**applied only once, after the final RS-tDCS session (the tenth session).

Primary outcome measures:

Page 5 of 22 Version Date: 10/09/2023 1. Feasibility of the intervention – number of completed remotely supervised transcranial direct current stimulation (RS-tDCS) sessions, for both active and sham groups:

We expect at least 70% of the subjects to complete at least 5 of recommended 10 RS-tDCS sessions within three weeks of receiving the home-based tDCS device.

This criterion is based on a study that reported dropout rates between 22% and 25% of homebased tDCS for patients with bipolar depression (40) and that therapeutic effects with tDCS could be achieved within one week of treatment (24).

Secondary outcome measures:

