7. The level of side effects will be assessed at the end of each session on a 0 (not at all) to 10 (highest degree) scale used by Ahn et al. (2019) (37), which includes the following symptoms: 1. Itching; 2. Burning; 3. Headache; 4. Fatigue; 5. Nervousness; 6. Dizziness; 7. Difficulty concentrating. The total score is the sum of the 7 items, varying from 0 to 70. Higher scores indicate higher levels of side effects.

8. Treatment emergent event review: after each RS-tDCS session and clinical assessment, subjects will be asked "Have you had any new symptoms, new medical conditions or been started on new medication/treatment since we last saw you?". This information will help research staff to judge about potential adverse events related to the trial. In addition, changes in treatment will help researchers to account for them in data analysis and the study's results interpretation.

4.1. **STUDY INTERVENTION**

The study intervention is tDCS treatments delivered by the Soterix Medical mini-CT device (https://soterixmedical.com/research/remote/mini-CT). The device is a nonsignificant risk (NSR) device study because it does not meet the definition of a significant risk device under §812.3 (m) of the investigational device exemptions (IDE) regulation (21 CFR §812)

(https://www.accessdata.fda.gov/scripts/cdrh/cfdocs/cfcfr/CFRSearch.cfm?fr=812.3).

The Soterix Medical mini-CT device for the RS-tDCS includes: (1) 1 x 1 mini-CT tDCS device; (2) SNAPstrap headgear, a "cap"-like placement for simple positioning and uniform electrode placement; (3) SNAPpads (individually-packaged pre-moistened sponge), and snap connectors (Figure 1) (39).

[figure not shown]

Figure 1. Remotely supervised (RS-tDCS) Equipment. (1) 1 x 1 mini-CT tDCS device; (2) SNAPstrap headgear: "cap"-like placement for simple positioning and uniform electrode placement; (2a) markers for guidance in placement; (2b) electrode polarity labeling with fixed wiring. (3) SNAPpad: (3a) individually-packaged pre-moistened sponge; perforated packaging for easy opening; (3b) snap connectors. (adapted from Pilloni, G., A. et al., Brain Stimul 15(3): 707-716, http://creativecommons.org/licenses/by-nc-nd/4.0/, DOI: 10.1016/j.brs.2022.04.014). The figure at the bottom simulates an RS-tDCS session.

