device, how to turn it on/off, and insert the unlock codes for one-time use; 2) to assess if the subject tolerates the protocol electric current through the tolerability test; 3) answer any questions the subjects may have. As the Soterix Medical mini-CT device will be with the subjects during the RS-tDCS sessions, subjects will be asked to sign an IRB-approved device loan agreement at the baseline.

Clinical questionnaires will be re-administered at day 14 [+ 7 days], day 30 [+ 7 days], and day 60 [+ 10 days] from the first RS-tDCS session session15 (Figure 3). While we aim to reach subjects on the phone for follow-up, research staff may email or text subjects to schedule the RS-tDCS sessions and clinical assessments. Subject identifying information and protected health information (PHI) is not exchanged in the text messages themselves. Detailed information about text messaging is included under the "Privacy and Confidentiality of Subjects and Research Data" section. Security risks associated with text messaging are described in detail during consent.

After baseline assessment, research staff not involved in the RS-tDCS supervisions and clinical assessments will randomize the subject to active or sham control group and set up the device condition (active or sham), program the intensity for the active condition (either 2.0 mA or 1.5 mA, according to the tolerability test) and duration (30 minutes) of each session, and get the device unlock codes for one-time use to be provided by the research staff to the subject immediately before each session. The discharge day will be tracked daily by the research staff through the electronic hospital medical record. Once the subject is discharged, research staff will deliver the RS-tDCS device by mail to the subject's address in a pre-paid FedEx package to send it back and contact the subject once the device has arrived at their home (by using the mail tracking number) to schedule the first RS-tDCS session.

*device set up for the condition (active or sham), and locked (unlock codes for one-time use will be provided before each session); **day 1 being the first RS-tDCS session and no sessions on weekends. CPEP: Comprehensive Psychiatric Emergency Program; DLPFC: dorsolateral prefrontal cortex; RS-tDCS: remotely supervised transcranial direct current stimulation.

RS-tDCS sessions:

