Research staff with training in using home-based tDCS by the Soterix Medical will meet with the subject via HIPAA-compliant videoconference previously scheduled. Subjects will be encouraged to find a distraction-free setting to complete treatment sessions. After guiding the subject with the proper adjustment of the SNAPstrap headgear and turning on the 1 x 1 Mini-CT device, research staff will provide the device unlock codes for one-time use to the subject. All ten device unlock codes for one-time use (one for each tDCS session) are obtained previously, just after the device is programmed to active or sham. The device unlock codes for one-time use allow the device to function only once a day, just after the inclusion of the code, with the level of electric current and duration of the session determined by the protocol, both (electric current level and duration of the session) pre-programmed on the device before it is delivered to the subject. Thus, the subject cannot alter the electric current level, the duration of the session, or use the device more than once a day. After each RS-tDCS session, research staff will apply the side effects questionnaire, review the subject's current treatment ("treatment review"), ask about any new or updated mental or physical symptoms since the last assessment (adverse events review), and apply the C-SSRS - screening version (C-SSRS SV) as part of the risk assessment (please, see more details on item "9. RISK TO SUBJECTS"). After the last RS-tDCS session (the tenth session), research staff will apply the feasibility questionnaire and blinding assessment. (Table 1). To assess blinding, the subjects will be asked the following question, "What treatment do you believe you have received??"(47). There will be three possible answers: 1) "active-tDCS"; 2)

"sham-tDCS" or 3) "Don't know". If the answer is "Don't know", research staff will ask "Would you be willing to provide your best guess about the treatment you received?", and could choose from two possible replies: 1) active-tDCS; 2) sham-tDCS (47, 48). We will use the Bang Blinding Index, which varies from -1 to +1, being 1 complete lack of blinding, +1 the opposite guessing, and 0 being related to perfect blinding (48). After the tenth session, the subject will be asked to send back the equipment in the pre-paid mail package to send it back.

Clinical assessments:

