Clinical assessments with be performed at day 14 [+ 7 days], day 30 [+ 7 days], and day 60 [+ 10 days] from the first RS-tDCS session with the questionnaires described in Table 1. Thus, the duration of and individual's participation in the study will be up to 70 days.

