- research staff will also communicate with the unit staff in case of any concerns about the subject during the baseline assessment.
- For this assessment, the following questions will be added, and the research staff must provide the answers ("yes" or "no"): "Active ideation with plan and intent *currently*?"; "Are you otherwise concerned about the patient at all?"

b) at the RS-tDCS sessions:

- after the C-SSRS screening version assessment, research staff will ask the subject if there is current active suicidal ideation with plan and intent. If the subject reports current active suicidal ideation plan and intent, research staff will inform the subject that they need to communicate this information (about the active suicidal ideation with specific plan and intent) to a licensed clinician from the research team to discuss the need for a specialized assessment.
- research staff will also communicate the licensed clinician in case of any concerns about the subject during the RS-tDCS sessions.
- For this assessment, the following questions will be added, and the research staff must provide the answers ("yes" or "no"): "Active ideation with plan and intent *currently*?"; "Are you otherwise concerned about the patient at all?"

c) at the clinical assessments (day 14, day 30, and day 60 from the first RS-tDCS session):

- after the C-SSRS assessment, research staff will ask the subject if there is current active suicidal ideation with plan and intent. If the subject reports current active suicidal ideation plan and intent, research staff will inform the subject that they need to communicate this information (about the active suicidal ideation with specific plan and intent) to a licensed clinician from the research team to discuss the need for a specialized assessment.
- research staff will also communicate the licensed clinician in case of any concerns about the subject during the follow-up assessments.
- For this assessment, the following questions will be added, and the research staff must provide the answers ("yes" or "no"): "Active ideation with plan and intent currently?"; "Are you otherwise concerned about the patient at all?"

The licensed clinician will follow the best policies and procedures of URMC and applicable state law for providing resources and determining if emergency evaluation is required. At minimum, the licensed clinician will:

- Advise the subject about emergency contact number

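### The dated suicide-risk and adverse-event questions after discharge all hang on the first session, so a randomised subject who never starts has no datable study screen

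*Combined protocol and SAP*

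**What the plan says.** The protocol has two routes for asking about suicide risk and adverse events after discharge.

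- **After a session.** Section 8 has staff "apply the C-SSRS - screening version (C-SSRS SV) as part of the risk assessment". Section 9(b) adds that "after the C-SSRS screening version assessment, research staff will ask the subject if there is current active suicidal ideation with plan and intent".
- **At a clinical assessment.** Section 8 sets these for day 14 (+7), day 30 (+7) "and day 60 [+ 10 days] from the first RS-tDCS session with the questionnaires described in Table 1". Section 4 defines the first as "post-treatment day 14 (14 days after the first RS-tDCS session"). Section 9(c) attaches the plan-and-intent question to these visits.

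The adverse-event question uses the same two occasions: "after each RS-tDCS session and clinical assessment, subjects will be asked" (Section 4, secondary outcome 8).

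Under Section 8, randomisation follows the in-hospital baseline. The device is mailed after discharge, and staff then "contact the subject once the device has arrived at their home (by using the mail tracking number) to schedule the first RS-tDCS session". The primary feasibility criterion uses a different clock. It asks that subjects "complete at least 5 of recommended 10 RS-tDCS sessions within three weeks of receiving the home-based tDCS device" (Section 4).

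Section 16 compares the arms on adverse events with Fisher's exact test and counts every subject in that comparison.

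**The concern.** Feasibility time starts at device receipt. The safety calendar starts only if a first session takes place. A subject can be randomised, discharged and sent a device, and never begin. Such a subject counts against feasibility, but the plan gives no date on which anyone from the trial asks about suicidal ideation or adverse events.

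The protocol's own background treats this as the dangerous period. Section 2 cites a review in which about a fifth of suicides and attempts fell within 15 days of discharge. It also cites poor outpatient engagement after emergency discharge as a reason for the study.

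The safety data are affected too. Subjects who attend a later visit can still report earlier events, because the question covers the time since last contact. A never-starter has no such visit. If all subjects are counted in the adverse-event comparison, that subject could appear event-free because no question was scheduled. The listing is then less complete for planning the full trial.

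**Working it through.** **Reproducing the plan's figure.** Section 8 gives participation as up to 70 days. Day 60 plus its 10-day window is 60 + 10 = 70. The figure matches when the count starts at the first session, which confirms the anchor.

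**Never-starter.** Every post-discharge screen needs either a session or a date counted from the first session. With no first session there are none. The call after delivery is described only as scheduling.

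**Early stopper.** Inputs are the day 14 window (day 14 to day 21, Section 8) and the note to Figure 3, "day 1 being the first RS-tDCS session and no sessions on weekends". I assume one session per weekday up to the stop.

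- Shortest gap = 14 − latest possible day of the last session.
- Longest gap = 21 − earliest possible day of the last session.

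With the first session as day 1:

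| Stops after session | Last session on day | Gap to day 14 visit (days) |
|---|---|---|
| 1 | 1 | 14 − 1 = 13 to 21 − 1 = 20 |
| 2 | 2 to 4 | 14 − 4 = 10 to 21 − 2 = 19 |
| 5 | 5 to 7 | 14 − 7 = 7 to 21 − 5 = 16 |
| 10 (completes) | 12 to 14 | 14 − 14 = 0 to 21 − 12 = 9 |

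Section 4 instead counts 14 days after the first session, which adds one day throughout: 14 to 21 after session 1, and 8 to 17 after session 5. If the day 14 visit is also missed after a stop at session 1, the gap is 30 to 37 days (29 to 36 with session 1 as day 1). For comparison, consecutive weekday sessions are at most 3 days apart.

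**Late starter.** Take receipt as day 0 and require five weekday sessions by day 21. The latest qualifying first session is then day 15 (receipt Monday to Thursday), day 17 (Friday) or day 16 (Saturday). Such a subject can meet the feasibility criterion with no scheduled screen for the first 15 to 17 days after receipt.

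**How many.** The documents give no rate of never starting. If that rate is q, the chance of at least one among 20 is 1 − (1 − q)^20. For assumed values of 1%, 5% and 10% this is 18%, 64% and 88%. The feasibility rule needs 0.70 × 20 = 14 subjects, so it tolerates 20 − 14 = 6 with fewer than five sessions. That is a tolerance and not a forecast.

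**The case against.** The plan does not leave these subjects unattended:

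- Section 9 requires consent to remain in outpatient mental health care and provides a safety plan for enrolled inpatients.
- Section 5 requires a contact person, expressly for safety or when the subject cannot be reached, and residence in the Mobile Crisis Team's area.
- Section 14 allows emails, letters, calls and a survey link to maintain contact, and states that well-being is monitored.
- Section 16 refers to hospital crisis protocols already in place.

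All of this stands. It rules out saying that monitoring as a whole lapses. What lapses is the trial's own scheduled screening, because none of these safeguards has a date or is triggered by sessions not happening.

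A reader might infer that early stoppers and late starters also fall outside the safety calendar. They do not. Both have had a first session, so days 14, 30 and 60 can be dated. The early stopper's gap is temporary and shrinks with each session completed, and the late starter's calendar is only shifted.

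A reader might also infer a number of missed events from the cited 20%. That figure is a share of events in another population and not an absolute risk, so it gives no count for 20 subjects. Nor do the documents show that missing sessions signals clinical deterioration.

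Finally, a reader might conclude that weekly safety calls are needed whenever sessions stop. Such calls could prompt sessions and so act on the primary outcome. One subject is 5 percentage points, and moving from 13 to 14 of 20 reverses the feasibility verdict. A call at day 7 after receipt leaves 14 days of the three-week window. Making the calls equally in both arms does not remove this, because feasibility is judged on all subjects together.

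**Conclusion.** The point holds for scheduled study screens. A randomised subject who never starts has none that can be dated. A subject who stops at session 1 waits 14 to 21 days (13 to 20 with session 1 as day 1), and one who stops at session 5 waits about 7 to 16. A late starter has no scheduled screen before the first session.

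This is more than missing detail: following the stated dating rule leaves never-starters without scheduled trial safety follow-up, although the adverse-event comparison counts them. The number affected is unknown and may be zero. The conclusion rests on the visible text. Figure 3, the pages removed before review and the consent form could not be checked, and any of them might contain a fallback. Given the safeguards outside the schedule, I place this between a suggestion and a firm recommendation.

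**What to change.** 1. **Fallback date (Section 8, Clinical assessments).** If no first session has occurred, date the day 14, 30 and 60 safety assessments from device receipt, or from discharge if the device is never received. Each would comprise the C-SSRS, the plan-and-intent question and the adverse-event question. If a first session follows, the protocol's own dating takes over, and any assessment already done counts as safety data only.
2. **Record review (Section 16).** When the day 60 window closes, review the hospital record of every randomised subject who has not withdrawn for readmission, emergency visit, self-harm and death. Add these events to the adverse-event listing by arm, and report the number with incomplete contact. Section 7 already authorises record access but schedules no follow-up use, so confirm that the consent wording covers this.

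**Cost.** Item 1 needs no new tracking, since receipt is already followed by mail tracking number. It adds up to three remote assessments per never-starter, or 3 × $30 = $90 each if paid on Section 12 terms. If all six tolerated non-completers never started, that would be 6 × 3 = 18 assessments and 6 × $90 = $540. Item 2 is at most 20 record reviews.

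**Limits.** The period while the device is in the mail stays unscreened, and the early stopper's temporary gap is not shortened. Events treated outside this hospital system, or occurring after withdrawal, are still missed.

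**Optional.** A brief safety contact after 7 days without a session, repeated weekly, would shorten the gaps. The sponsor should weigh it against its possible effect on session completion and describe it with the feasibility result if it is adopted.

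### The Bang Blinding Index is given a wrong anchor at +1, so a non-zero blinding result could be read backwards

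*Combined protocol and SAP*

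**What the plan says.** Section 8 (Study Procedures), under the RS-tDCS sessions, describes the blinding assessment. Each participant is asked "What treatment do you believe you have received" and may answer active, sham or don't know. Those who do not know are then asked "Would you be willing to provide your best guess about the treatment you received", with active and sham as the choices. The answers are to be summarised with the Bang Blinding Index, described as follows: "which varies from -1 to +1, being 1 complete lack of blinding, +1 the opposite guessing, and 0 being related to perfect blinding".

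The footnote to Table 1 in Section 4 adds only the timing: the question is "applied only once, after the final RS-tDCS session (the tenth session"). Section 17 (Data Analysis Plan) does not mention blinding or the index. The sentence in Section 8 is therefore the only guidance on how to read the result. It cites a methods reference but gives no formula.

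**The concern.** The size of the index shows how far guesses depart from chance, and its sign shows the direction. A positive value means participants tended to identify their treatment. A negative value means they tended to name the other one. These lead to different conclusions about whether the sham worked, so the rule for reading the sign has to be right.

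The rule in Section 8 attaches opposite guessing to +1, the value that all-correct guessing produces. An author who followed that anchor would report unblinding as its reverse.

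The result has a use in this trial. Section 4 describes the study as double-blind, Section 1 (Aim 1) includes the feasibility of the sham protocol for future use, and Hypothesis 2 looks to an active-versus-sham difference in reported ideation to size a full trial. Whether participants believed the sham bears on all three.

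Either sign could occur. Sections 2, 4.1 and 9 cite similar rates of tingling, itching and warmth under active and sham stimulation, so sham participants may believe they had active treatment, which gives a negative sham-arm index. On the other side, every participant feels real current in the tolerability test at orientation (Section 8), which could help some guess correctly. The documents hold no data on guesses, so these are possibilities, not predictions.

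**Working it through.** **Inputs**
- Range and anchors: Section 8, as quoted above.
- Number per arm: 20 randomised (Section 4) at 1:1 (Section 4.1), so 20/2 = 10. The plan does not state a per-arm number.
- Formula: the documents give none, so the standard definition of the named index is used. Within one arm, index = (correct − opposite)/n, where n counts everyone who answered, including any remaining don't-know answers.
- The splits of guesses below are assumed, for illustration.

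**Step 1. The anchors, in an arm of 10**

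| Guesses in the arm | Calculation | Index | Meaning attached in Section 8, as printed |
|---|---|---|---|
| 10 correct, 0 opposite | (10 − 0)/10 | +1 | two opposite meanings (1 and +1) |
| 5 correct, 5 opposite | (5 − 5)/10 | 0 | perfect blinding (right) |
| 10 don't know | (0 − 0)/10 | 0 | perfect blinding (right) |
| 0 correct, 10 opposite | (0 − 10)/10 | −1 | none |

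The range and the zero anchor reproduce. The anchor for opposite guessing does not: it belongs at −1.

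**Step 2. Could PDF reading explain it?** A minus sign may have been lost before the first 1.
- If nothing was lost, 1 and +1 are the same number with contradictory meanings, and −1 has no meaning.
- If a minus was lost, complete unblinding sits at −1 and opposite guessing at +1, so both ends are reversed.

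The text cannot show which applies, but the +1 anchor is wrong under both.

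**Step 3. Effect on plausible results**
- 9 of 10 correct: (9 − 1)/10 = +0.8, strong unblinding. The printed 1 anchor reads this correctly; the +1 anchor reads it as mostly opposite guessing.
- 1 of 10 correct: (1 − 9)/10 = −0.8. The printed text has no anchor at this end.
- 8 of 10 in each arm believe they had active treatment. Active arm: (8 − 2)/10 = +0.6. Sham arm: (2 − 8)/10 = −0.6. Correctly read, both arms lean towards active. With the two ends swapped, both would be read as leaning towards sham.
- The question comes only after the tenth session, so fewer than 10 per arm may answer. With 7 answers, 6 of them correct: (6 − 1)/7 = +0.71, and the same ambiguity applies.

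**Step 4. Allowing for don't-know answers**
- With 6 correct, 2 opposite and 2 left as don't know: (6 − 2)/10 = +0.4. The mirror image gives −0.4.
- If best guesses after don't know are given an assumed weight of 0.5, then 6 firm and 2 best guesses correct against 1 firm and 1 best guess opposite gives [(6 + 0.5 × 2) − (1 + 0.5 × 1)]/10 = 5.5/10 = +0.55. With correct and opposite exchanged it is −0.55.

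The size changes with the handling of don't-know answers. The sign does not.

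**The case against.** The strongest reply is that, as printed, the sentence nearly corrects itself. It names a standard index, gives the right range and zero point, gives a correct meaning to the first 1, and cites the method. As 1 is already used and the range includes −1, a reader can infer that the second anchor should be −1. An analyst holding the guess counts would also see directly whether participants were right. On this view the defect is a one-character slip, and a consistent backwards reading needs the lost minus sign, which cannot be shown.

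Part of this stands. The swapped-ends case is conditional, and an analyst who knows the index would probably read it correctly. But the reply depends on the reader overriding the written rule, and no other section does so. If the minus sign was lost, the sentence is internally consistent and gives no warning that it is wrong.

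Other points are fair and limit the weight of the concern. The formula comes from the standard definition, not from the documents. The illustrative counts are assumed. Similar sensations in the two arms fit an index near zero as well as a negative one, and a value near zero is read correctly. Nothing else in the plan depends on the index.

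**Conclusion.** The concern holds, as a minor point. The anchor at +1 is wrong on either reading of the sentence: the printed text contradicts itself, or its two ends are reversed. A strongly unblinded arm, for example +0.8 from 9 of 10 correct, could be reported as opposite guessing, and a negative value either has no stated meaning or is read the wrong way round. A value of 0 is not affected.

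The consequence is limited. The calculated index does not change, it is not among the primary or secondary outcomes in Section 4, no decision rule uses it, and the feasibility criterion and sample size are untouched. The conclusion rests on the standard per-arm definition of the index. The numerical examples also assume 10 per arm (or 7 answering) and the stated splits of guesses; the direction of the error depends on none of these.

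**What to change.** Replace the interpretive part of the sentence in Section 8 with corrected anchors: +1 when all participants in an arm guess their treatment correctly (no blinding), 0 when guessing is random (consistent with blinding), and −1 when all guess the opposite treatment. State in the same sentence that the index is calculated and reported separately for the active and sham arms, since the sign is interpreted within an arm.

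The cost is one corrected sentence. It needs no new data, leaves the questions put to participants as they are, and does not alter any calculated value.
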